## 1. Rationale

Colorectal cancer (CRC) accounts for approximately 10% of all cancers diagnosed worldwide. Numerous studies have shown that CRC screening using the faecal occult blood test (FOBT) can reduce mortality; however, the procedure is also associated with certain drawbacks, including false negatives and false positives, overdiagnosis, overtreatment, and potential complications from colonoscopy. Therefore, the decision to undergo or not undergo screening should be an informed one.

To support this process, Decision Aids (DAs) have proven useful. These are decision-support tools designed to help individuals make informed choices about their health.

The scientific literature reports several studies related to cancer screening tests, which in some cases have been associated with increased adherence to screening programs. In Italy, where three national screening programs are currently active (CRC, breast cancer, and cervical cancer), only a recent development of a DA specifically for mammography screening has been documented.

To ensure that the decision to undergo FOBT screening is well informed, the use of a smartphone application has been proposed as a supportive tool. Such an application can also serve as a platform to assess the effectiveness of new communication strategies—such as tailoring language to educational level and adapting content feedback based on Locus of Control (i.e., the extent to which individuals believe that life events are determined by their own actions or by external factors beyond their control)—as well as elements of Gamification, a relatively new approach that applies game mechanics to non-game contexts to enhance user engagement. This technique introduces an element of enjoyment into routine activities, which can increase motivation and knowledge—in this case, serving as a tool to promote primary prevention and healthy lifestyle behaviours.

The use of eHealth, particularly smartphone-based applications, has been increasingly documented in the literature as effective across various clinical fields.

## 2. General Objective of the Study

The general objective of this study is to evaluate the impact of a mobile application on informed decision-making regarding participation in colorectal cancer screening among individuals who will receive their first invitation to undergo the faecal occult blood test (FOBT), residing in the area covered by Brescia LHA.

Secondary objectives include assessing the impact of using the application on screening adherence rates, evaluating decision conflict, customer satisfaction, and the acceptability of a smartphone

application, as well as examining its effectiveness in conveying information about primary prevention and healthy lifestyle behaviours.

## **2.1. Primary Objective**

To evaluate the impact of using a smartphone application on users' awareness and understanding regarding colorectal cancer prevention.

## **2.2. Secondary Objectives**

1. To assess and compare screening adherence rates between the two study arms.
2. To assess and compare, between the two study arms, the level of knowledge related to healthy behaviours and primary prevention.
3. In the intervention arm, to evaluate decision conflict, customer satisfaction, and the acceptability of the mobile application.

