### **3.2. Secondary Endpoint**

1. Screening adherence rate, calculated as the ratio between the number of individuals who completed the screening and the total number of individuals invited to participate in the screening program in the two study arms.
2. Level of knowledge related to healthy behaviors and primary prevention in the two study arms will be measured using a digital questionnaire containing 13 questions on primary prevention and healthy lifestyle behaviors.
3. Decision conflict, customer satisfaction, and the acceptability of the application will be assessed through additional questions included in the same digital questionnaire.

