### 6.1. Intervention Procedures

All subjects who meet the inclusion criteria will receive, through an attachment to the invitation letter (Annex 1) for screening, the instructions on how to download the application on their smartphone. Once downloaded, the application will allow exclusively to complete the informed consent (Annex 2), to read the privacy policy (Annex 3) and subsequently the baseline questionnaire (T0) (Annex 4), in digital format. Afterwards, the users will be progressively randomized into an intervention arm and a control arm. Recruitment will be stopped upon enrollment of subject number 2500.

Subjects assigned to the control arm will have access to the mobile application in a limited version. In a specific section, there will be standardized and digitalized scientific dissemination documents aimed at providing information on primary prevention, healthy and correct lifestyles, and on colorectal cancer screening.

Subjects assigned to the intervention arm will have access to the full version of the application. In particular, in addition to the specific section available for the control group, users will be presented with the aforementioned information in the form of daily “pills.” Moreover, by completing one quiz per week and one twice a week, the user will be able to earn points based on the number of correct answers provided. The quizzes will be of two types: the first, weekly, will consist of 10 questions, 5 regarding primary prevention topics and 5 on general knowledge; the second, every 3 days, will consist of 3 prevention-related questions. Users will have 15 seconds to answer each question, and the score, in case of a correct answer, will be assigned based on the time taken to select it.

For both arms, it will be possible to fill in a follow-up questionnaire at T1 and T2 (Annex 5), respectively at 3 and 6 months from enrollment.

The project foresees a total duration of 30 months.

It is possible to identify three main phases:

**Phase 1**, called **Project Start-Up**, consists of:

- 1.1 Drafting of the Study Protocol
- 1.2 Design of the CRF, creation of the electronic database and related completion manual
- 1.3 Definition of the Statistical Analysis Plan (SAP)
- 1.4 Preparation and submission of the documentation to the relevant Ethics Committee

**Phase 2**, called **Study Set-Up**, includes:

- 2.1 Identification of the cohort, patient enrollment and randomization

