3.1 Data analysis and dissemination of results (publications and conference materials)

## 6.2. Data Collection Tool

Two digital questionnaires (to be completed directly within the App) will be used: one at time T0 (baseline) and the second at time T1 (three months) and T2 (six months). In particular:

1. Within the questionnaire administered at baseline, the validated Multidimensional Health Locus of Control (MHLC) questionnaire is included. It contains eighteen questions through which the Locus of Control of the participants will be assessed.
2. Informed choice will be evaluated through three items: knowledge (score of at least 7 out of 13), attitude (score > 24), and intention (actual behaviour). Among these, the first two items must necessarily be satisfied in order to define that the subject is informed about the choice.
3. The level of knowledge related to healthy behaviours and primary prevention will be assessed through the 13 questions on primary prevention and healthy lifestyle behaviours. Based on the number of correct answers, subjects will be classified into three categories: low knowledge (0 to 5 out of 13), good knowledge (6 to 8 out of 13), and excellent knowledge (9 to 13 out of 13).
4. Decision conflict, customer satisfaction, and the acceptability of the App will be assessed at T1 and T2 through specific items of the second questionnaire (decision-making process, satisfaction, and decision-aid acceptability).

In addition, Brescia LHA will provide data on residents born in 1973 and 1974, by sex, and the number of subjects, by sex, who actually completed the FOBT screening.

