## 7. Study Duration and Planned Assessments

The duration of the study will be 30 months. The enrollment period will take place from January 2023 to August 2024, in conjunction with the invitation sent by Brescia LHA to citizens born in 1973 and 1974 to undergo FOBT screening. Following the completion of the informed consent and the baseline questionnaire, users will be progressively randomized.

The total enrolment period will last 20 months. Assessments for each subject will be performed at baseline (T0), at 3 months (T1), and at 6 months (T2).

**T0:** questionnaire collecting information on socio-demographic data, risk perception, knowledge, attitude, intention, and Locus of Control.

**T1:** questionnaire collecting information on risk perception, knowledge, attitude, intention, decision-making process, customer satisfaction, and application acceptability.

**T2:** same questionnaire administered at T1.

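### Objective 3 evaluates decision conflict in the intervention arm only, although the follow-up questionnaire is offered to both arms and the control arm is the only comparator

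*Combined protocol and SAP*

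**What the plan says.** Section 2.2 lists three secondary objectives. The first two are comparative; item 2, for example, reads "To assess and compare, between the two study arms, the level of knowledge related to healthy behaviours and primary prevention". Item 3 changes form: "In the intervention arm, to evaluate decision conflict, customer satisfaction, and the acceptability of the mobile application".

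Other sections do not carry that limit. The general objective in Section 2 lists the same three outcomes with no arm named. Endpoint 3 in Section 3.2 reads "Decision conflict, customer satisfaction, and the acceptability of the application will be assessed through additional questions included in the same digital questionnaire", and the questionnaire it refers back to is the one that measures knowledge in both arms under endpoint 2.

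On data collection, Section 6.1 states "For both arms, it will be possible to fill in a follow-up questionnaire at T1 and T2". Section 6.2 describes only two questionnaires, one for baseline and one for T1 and T2, and places the items in the latter: "Decision conflict, customer satisfaction, and the acceptability of the App will be assessed at T1 and T2 through specific items of the second questionnaire". Section 7 includes "decision-making process, customer satisfaction, and application acceptability" in the T1 content, with no arm restriction, and makes T2 the same questionnaire.

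Section 8.2 names a chi-square test between arms for informed choice and for adherence, and a Friedman test for knowledge scores over time. For decision conflict, satisfaction and acceptability it offers only general descriptive statistics.

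**The concern.** The general objective is to learn what the app does to informed decision-making about screening, and the rationale places the app among decision aids. Decision conflict bears directly on that aim, and it has the same meaning in both arms because all participants face the same screening decision after the same invitation.

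Read as written, objective 3 yields a level of decision conflict among users of the full app and nothing to set it against. A low score could come from the app, from the standard information that both arms can read, or from the kind of person who downloads an app and consents. If the comparison is not pre-specified, any later one will be post hoc. The sections also disagree on scope, which needs reconciling whichever reading the sponsor intends.

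**Working it through.** **1. Scope, section by section**

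| Place | Arm named for these outcomes | Comparison named |
|---|---|---|
| Section 2, general objective | none | none |
| Section 2.2, item 3 | intervention only | none |
| Section 3.2, item 3 | none | none |
| Sections 6.1, 6.2 and 7 | one T1/T2 questionnaire, offered to both arms | not applicable |
| Section 8.2 | none | none |

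Only Section 2.2 restricts the arm.

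**2. Is there another comparator?** Section 7 gives the T0 content as sociodemographic data, perceived risk, knowledge, attitude, intention and locus of control. The decision-process, satisfaction and acceptability items first appear at T1. A change from baseline within the intervention arm is therefore not available, which leaves the control arm.

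**3. The plan's own sample size.** Inputs from Section 8.1: 50% against 60%, two-sided 5%, 90% power. With pooled variance under the null and no continuity correction:

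n = [1.95996 × √(2 × 0.55 × 0.45) + 1.28155 × √(0.5 × 0.5 + 0.6 × 0.4)]² / 0.10² ≈ 518.04, rounded up to 519 per group.

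This reproduces the stated figure. It is the requirement for the primary endpoint. No calculation is given for decision conflict.

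**4. What a between-arm comparison could detect.** The documents give no instrument, scoring or SD for decision conflict, so the result is in SD units. Assumptions: 1:1 allocation (no ratio is stated) and 519 respondents per arm.

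- 80% power: (1.96 + 0.842) × √(2/519) = 0.174 SD
- 90% power: (1.96 + 1.282) × √(2/519) = 0.201 SD
- Half-width of the 95% CI: 1.96 × √(2/519) = 0.122 SD

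**5. Range over the unknown response count.**

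- The recruitment cap of 2,500 less 20% drop-out gives 2,500 × 0.8 / 2 = 1,000 per arm. The detectable difference is then 2.802 × √(2/1,000) = 0.125 SD at 80% power and 3.242 × √(2/1,000) = 0.145 SD at 90%.
- If only half of the 519 answered, the figures in step 4 grow by √2, to about 0.25 and 0.28 SD.

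**The case against.** The strongest reply is that objective 3 is deliberately descriptive. Two objectives are worded as comparisons and the third is not, and describing how users of a product rate it is a legitimate secondary aim. For satisfaction and acceptability this largely stands. Control subjects have a limited version of the app, so the arms would be rating different products, and questions about quizzes or daily pills have no meaning for controls. It does not stand for decision conflict, which concerns the screening decision rather than the app.

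A second reply is that the control data may not exist. Section 6.1 says only that the questionnaire can be filled in, not that everyone will complete it. Endpoint 3 calls the items additional questions, and an in-app form could show them to one arm only. Annex 5 is not among the documents, so this cannot be checked. The text describes a single questionnaire with no arm-specific version, so availability in both arms is the natural reading, but it remains an inference.

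A reader might go further and infer that control responses already in hand are being thrown away. The documents do not support that. Nothing says that control answers will be dropped, and Section 8.2 applies descriptive statistics to the collected variables without naming an arm.

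Finally, 519 is a sample-size requirement and not a forecast of respondents, and without a scale or a minimum important difference nobody can say whether 0.17 to 0.20 SD matters. Both points are correct, so the figures serve as illustration only.

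**Conclusion.** The point holds for decision conflict. One objective is narrower than the general objective, the endpoint and the data collection around it. As written, the trial could report a level of decision conflict but no effect of the full app on it, since there is no baseline measure and no planned comparison. This is a gap in a secondary outcome; the primary analysis and the sample size do not change.

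The size is illustrative: about 0.17 SD detectable at 80% power and 0.20 SD at 90%, given 1:1 allocation and 519 respondents per arm. The conclusion also assumes that control subjects are shown the decision-conflict items.

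The wider reading, that all three outcomes need a formal between-arm test, goes too far. For satisfaction and acceptability, a description by arm is enough.

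**What to change.** 1. Check Annex 5 and the control version of the app to confirm that control subjects see the decision-conflict items. If they do not, either show the items to both arms or state that the objective is a one-arm description, and align Sections 2 and 3.2 with it.
2. If they do, reword objective 3 and endpoint 3 so that decision conflict is compared between arms at one pre-specified time point, for example T1, with T2 supportive.
3. Name the decision-conflict instrument and its scoring; Section 6.2 refers only to specific items.
4. Add one analysis to Section 8.2: the between-arm difference in that score with a 95% CI, by assigned arm. Fix the method in advance, not after seeing the distribution. Label it exploratory, with no multiplicity control, and report the number of respondents in each arm.
5. Report satisfaction and acceptability descriptively by arm, as full against limited app. Keep questions on quizzes and pills as intervention-arm description.

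The cost is a few sentences in Sections 2.2, 3.2, 6.2 and 8.2, one extra exploratory analysis, and the work of settling the decision-conflict score. If step 1 is confirmed, no further recruitment or questionnaire items are needed.

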## **3. Endpoint**

### **3.1. Primary Endpoint**

The primary endpoint is users' awareness in the field of cancer prevention, specifically regarding colorectal cancer screening. This will be assessed as a dichotomous variable by combining measures of knowledge, attitudes, and intentions, according to the three-dimensional framework by Marteau et al. and comparing results between the two study arms. A participant will be considered to have made an informed choice if they have adequate knowledge and if their attitudes and behaviors are consistent. Among these three dimensions, adequate knowledge and consistent attitudes must be satisfied for the choice to be classified as "informed".

### **3.2. Secondary Endpoint**

1. Screening adherence rate, calculated as the ratio between the number of individuals who completed the screening and the total number of individuals invited to participate in the screening program in the two study arms.
2. Level of knowledge related to healthy behaviors and primary prevention in the two study arms will be measured using a digital questionnaire containing 13 questions on primary prevention and healthy lifestyle behaviors.
3. Decision conflict, customer satisfaction, and the acceptability of the application will be assessed through additional questions included in the same digital questionnaire.

## **4. Study Plan and Design**

Studio clinico randomizzato controllato monocentrico. I partecipanti allo studio verranno assegnati al braccio di controllo oppure di intervento mediante randomizzazione semplice, che prevede l'utilizzo di una sequenza di numeri casuali preparata dallo statistico, generati con il supporto del computer.

## **5. Inclusion and Exclusion Criteria**

Participants will be included in the study if they meet the following criteria:

- Male and female citizens born between January 1, 1973, and December 31, 1974, who turned 50 years of age in 2023 or will turn 50 in 2024, thereby becoming eligible for the national colorectal cancer screening program.
- Residents in the area covered by Brescia LHA.

- Individuals who have provided informed consent to participate in the study.

Participants without a smartphone will be excluded from the study

## 6. Intervention

Smartphone application not classified as a Medical Device.

### 6.1. Intervention Procedures

All subjects who meet the inclusion criteria will receive, through an attachment to the invitation letter (Annex 1) for screening, the instructions on how to download the application on their smartphone. Once downloaded, the application will allow exclusively to complete the informed consent (Annex 2), to read the privacy policy (Annex 3) and subsequently the baseline questionnaire (T0) (Annex 4), in digital format. Afterwards, the users will be progressively randomized into an intervention arm and a control arm. Recruitment will be stopped upon enrollment of subject number 2500.

Subjects assigned to the control arm will have access to the mobile application in a limited version. In a specific section, there will be standardized and digitalized scientific dissemination documents aimed at providing information on primary prevention, healthy and correct lifestyles, and on colorectal cancer screening.

Subjects assigned to the intervention arm will have access to the full version of the application. In particular, in addition to the specific section available for the control group, users will be presented with the aforementioned information in the form of daily “pills.” Moreover, by completing one quiz per week and one twice a week, the user will be able to earn points based on the number of correct answers provided. The quizzes will be of two types: the first, weekly, will consist of 10 questions, 5 regarding primary prevention topics and 5 on general knowledge; the second, every 3 days, will consist of 3 prevention-related questions. Users will have 15 seconds to answer each question, and the score, in case of a correct answer, will be assigned based on the time taken to select it.

For both arms, it will be possible to fill in a follow-up questionnaire at T1 and T2 (Annex 5), respectively at 3 and 6 months from enrollment.

The project foresees a total duration of 30 months.

It is possible to identify three main phases:

**Phase 1**, called **Project Start-Up**, consists of:

- 1.1 Drafting of the Study Protocol
- 1.2 Design of the CRF, creation of the electronic database and related completion manual
- 1.3 Definition of the Statistical Analysis Plan (SAP)
- 1.4 Preparation and submission of the documentation to the relevant Ethics Committee

**Phase 2**, called **Study Set-Up**, includes:

- 2.1 Identification of the cohort, patient enrollment and randomization
- 2.2 Data quality control and query resolution (completeness, accuracy and consistency analysis)
- 2.3 Progress meetings and related minutes

**Phase 3**, called **Statistical Analysis**, consists of:

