## 8. Statistical Aspects

### 8.1. Sample size

Based on previous studies, we considered an absolute difference of 10% between the proportion of individuals who make an informed choice and those who do not to be the minimum important difference for the sample size calculation. Assuming that the proportion of individuals making an informed choice is 50%, with a power of 90% and a two-sided significance level of 5%, 519 subjects per group are required, for a total of 1,038 subjects.

Considering an estimated colorectal cancer screening adherence rate of 50% in the province of Brescia and a probable drop-out rate of 20%, at least 2,492 subjects will need to participate in the study.

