## **8.2. Statistical Methods**

Descriptive statistics will be used to describe the collected variables: mean and standard deviation, median and interquartile range for quantitative variables, and absolute frequencies and percentages for qualitative variables. The comparison between the proportion of subjects making an informed choice in the two groups will be evaluated using the Chi-square test, as will the comparison between the proportion of subjects adhering to screening in the two arms.

Median scores obtained from the knowledge questionnaire will be evaluated using the Friedman test at the three time points.

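### The primary chi-square has no analysis set and no rule for missing questionnaires, so carrying it out on T1/T2 responders can bias the arm comparison in either direction

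*Combined protocol and SAP*

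**What the plan says.** - **Endpoint.** Section 3.1 defines informed choice as a binary outcome: "This will be assessed as a dichotomous variable by combining measures of knowledge, attitudes, and intentions". Section 6.2 gives the cut-offs: "Informed choice will be evaluated through three items: knowledge (score of at least 7 out of 13), attitude (score > 24), and intention (actual behaviour"). Knowledge and attitude must both be met.
- **Data source.** Section 6.2: "Two digital questionnaires (to be completed directly within the App) will be used". The local health authority supplies only counts by sex of residents and of people screened, which cannot give an individual's knowledge or attitude.
- **Follow-up.** Section 6.1 says that in both arms "it will be possible to fill in a follow-up questionnaire at T1 and T2", at 3 and 6 months. Neither visit is named as primary.
- **App content by arm.** Section 6.1: "Subjects assigned to the control arm will have access to the mobile application in a limited version". The intervention arm also gets daily information items and regular quizzes scored for points. Section 1 presents gamification as a means of raising engagement.
- **Baseline.** Sections 6.1 and 7 place consent and the T0 questionnaire before randomisation. T0 covers socio-demographic data, risk perception, knowledge, attitude, intention and Locus of Control.
- **Analysis.** Section 8.2: "The comparison between the proportion of subjects making an informed choice in the two groups will be evaluated using the Chi-square test". It gives no population, missing-data rule, use of T0 values in this comparison, or sensitivity analysis.
- **Drop-out.** Section 8.1 allows for "a probable drop-out rate of 20"% as an inflation of the sample size and takes it no further.

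**The concern.** The intervention works through the same channel that collects the outcome. Someone who stops opening the app gives no follow-up score, and one arm has been given more reasons to keep opening it. Who answers may therefore depend on arm, and within an arm on interest and knowledge, which are close to the endpoint itself.

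Inflating the sample size for drop-out restores precision but does nothing about selection. T0 values of the endpoint's own components exist for everyone randomised, and the stated test does not use them. At stake is whether an observed difference, or its absence, can be put down to the app rather than to who replied. The yardstick is the 10-point minimum important difference in section 8.1.

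**Working it through.** **The plan's own figures.** Two-sided 5% level, 90% power, 50% versus 60%, pooled variance under the null:

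n = [1.960·√(2·0.55·0.45) + 1.282·√(0.5·0.5 + 0.6·0.4)]² / 0.10² = 518.04, rounded up to 519 per group and 1,038 in total.

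Then 1,038 / 0.5 × 1.2 = 2,491.2, rounded up to 2,492. Recruitment stops at 2,500, or about 1,250 per arm. These figures reproduce. Drop-out enters only as the factor 1.2.

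**Formula for the responder comparison.** With true proportion informed p, and response probabilities r1 (informed) and r0 (not informed) in an arm:

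observed proportion = p·r1 / [p·r1 + (1 − p)·r0]

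Below, p = 0.5 in both arms, so there is no true effect. All response rates are assumptions; the documents give none by arm or by outcome.

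**Main illustration.** Control r1 = 0.80, r0 = 0.70; intervention 0.85 for both.
- Control: 0.40 / (0.40 + 0.35) = 53.3%. Intervention: 0.425 / 0.85 = 50.0%. False difference: −3.3 points, a third of the 10-point target.
- With 1,250 randomised per arm, responders number about 937 and 1,062. SE = √(0.533·0.467/937 + 0.25/1,062) = 0.0224. The shift is 1.49 SE, and P(|Z| > 1.96) is about 32%. Of this, 31.9% is against the app and 0.03% in its favour.
- With 519 responders per arm, SE = 0.0310, the shift is 1.08 SE, and the rate is about 19%.

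**Other patterns.**

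| Control r1/r0 | Intervention r1/r0 | Observed control | Observed intervention | False difference |
|---|---|---|---|---|
| 80/60 | 90/85 | 57.1% | 51.4% | −5.7 |
| 80/80 | 85/75 | 50.0% | 53.1% | +3.1 |
| 80/80 | 90/70 | 50.0% | 56.3% | +6.3 |
| 80/80 | 75/85 | 50.0% | 46.9% | −3.1 |
| 75/75 | 85/85 | 50.0% | 50.0% | 0 |
| 80/70 | 80/70 | 53.3% | 53.3% | 0 |

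Rows 2 to 4 have 80% response in both arms, which is the plan's own 20% loss, and are still biased. Row 5 has unequal response rates and is not. What matters is whether the relation between outcome and response differs by arm.

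**What the data alone allow.** Suppose 60% versus 50% is observed with 20% missing in each arm. The lowest possible difference among all randomised is 0.48 − (0.40 + 0.20) = −12 points. The highest is (0.48 + 0.20) − 0.40 = +28 points.

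**How far T0 imputation helps in the main illustration.** Assume one binary T0 predictor that splits the arm in half.
- 70% versus 30% informed at follow-up: imputed control estimate = ½[0.56/(0.56 + 0.21) + 0.24/(0.24 + 0.49)] = 52.8%, so 2.8 of the 3.3 points remain.
- 80% versus 20%: ½[0.64/(0.64 + 0.14) + 0.16/(0.16 + 0.56)] = 52.1%, so 2.1 points remain.

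**Counting missing as not informed.** In the same illustration this gives 0.5·0.85 − 0.5·0.80 = 42.5% − 40.0% = +2.5 points. That rule is not neutral either, and here it errs in the opposite direction.

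**The case against.** Most of the case on the other side concerns how much may be read into a silent plan, and most of it stands.

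- **A reader might infer that section 8.2 prescribes a responder-only analysis.** It does not. It names no population, and a chi-square on everyone randomised is possible if missing counts as not informed. What stands is an omission whose most natural execution is a responder comparison.
- **A reader might infer that follow-up is declared voluntary.** The wording in section 6.1 may describe only availability, and section 7 says assessments will be performed for each subject. Non-response is nevertheless expected, since section 8.1 plans for 20% loss.
- **A reader might infer that randomisation no longer protects the comparison, or that unequal response by arm is enough to bias it.** Neither follows. Two rows of the table show no bias, and the documents contain no response data.
- **A reader might take the 32% as a risk of falsely claiming benefit.** In that illustration nearly all of it runs against the app. Other assumed patterns favour the app, so the direction is unknown beforehand.
- **Imputation is no cure.** In the main illustration response depends on the follow-up outcome itself, and imputation from T0 leaves 2.1 to 2.8 of the 3.3 points. The other follow-up visit adds nothing for someone who missed both.

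The objection does not remove the central fact: the endpoint cannot be scored without the follow-up questionnaire, and the plan does not say what to do when it is absent.

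**Conclusion.** The concern holds as an omission with a foreseeable consequence. The analysis set and the missing-questionnaire rule are unspecified, and the obvious way of carrying out section 8.2 can be biased in either direction. Under response gaps of 10 to 20 points between informed and not-informed participants, the false difference is about 3 to 6 points against a 10-point target. The false-positive rate in the main illustration is 32% or 19%, depending on the number of responders.

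These sizes rest on assumed response rates, a true 50% informed in both arms, and a normal approximation. They show what could happen, not what will. The change is worth making because the mechanism is in the documents and the remedy costs analysis time only.

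**What to change.** In section 8.2:

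1. Name one follow-up visit, T1 or T2, as primary. Before the imputation model is fixed, state how the third component is measured, since section 6.2 equates intention with actual behaviour.
2. Analyse all randomised subjects in the arm assigned.
3. Impute missing components by multiple imputation within arm, from T0 knowledge, attitude, intention, Locus of Control and socio-demographic data and from the other follow-up visit.
4. Report as the main result a pooled risk difference, adjusted for T0 values, with a 95% confidence interval.
5. Add three sensitivity analyses: the responder-only chi-square, missing counted as not informed, and an arm-specific delta (tipping-point) analysis.
6. Report questionnaire response by arm at T1 and T2.

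The cost is more analysis work and a missing-at-random assumption behind the main result; no new data, visits or participants are needed. T0 data should be credited only with added precision and with less bias under that assumption. Because they cannot remove bias when response depends on the follow-up outcome, the plan should say that the conclusion also rests on the tipping-point result.
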